## 11.5 SAS Code

### 11.5.1 Primary analysis

```
ods output estimates=tests tests3=fixed;
proc mixed data=adef;
  where paramcd='FVC';
  class subjid trt01pn;
  model cfb = base areltn trt01pn trt01pn*areltn /ddfm=kr s residual outp=resplot;
  random intercept areltn / sub = subjid type = un;
  estimate 'Plc Slope' areltn 1 trt01pn*areltn 1 0/cl;
  estimate '3mg Slope' areltn 1 trt01pn*areltn 0 1/cl;
  estimate 'Slope 3mg v Plc' trt01pn*areltn 1 -1/cl;
run;
```

where

subjid = Subject ID

trt01pn = Randomized treatment group (1=Placebo, 2= GB0139 3mg)

base=Baseline FVC for the subject

areltn = Years since first dose

cfb = Change from baseline in FVC

<mean baseline FVC> = the mean of the variable base across all records in the dataset FVC relating to the population of interest (i.e. all records to be included in the model)

	Plus-Project Statistical Analysis Plan	
	Protocol Number: GALACTIC-1	Version: 1

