14.1 Statistical and Analytical Plans

A blinded data review will be conducted prior to database lock. This review will assess the accuracy and completeness of the study database, subject evaluability, and appropriateness of the planned statistical methods.

A statistical analysis plan (SAP) will be prepared and finalized prior to database lock. This document will provide further details regarding the definition of analysis variables and analysis methodology to address all study objectives.

For descriptive statistics categorical data will be presented as frequencies and percentages. Percentages will be based on the number of subjects with non-missing values for the corresponding categorical variable. Continuous data will be presented as number of subjects with non-missing values, mean standard deviation, median, minimum and maximum, as well as the 25th and 75th percentile.

All statistical tests as well as the confidence intervals will be two-sided. The study-wise type I error probability for the confirmatory analyses is set to 10%. 90% confidence intervals are to be calculated, if feasible.

Covariates for the primary analyses will be pre-specified. For secondary analyses these are anticipated to be broadly similar to primary analysis but will be fully specified in the Statistical Analysis Plan (SAP).

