14.4.1 Analysis of Primary Efficacy Endpoint

The primary endpoint is described in Section 9.1. The primary efficacy analysis is a random coefficient regression (random slopes and intercepts) model. Treatment and baseline FVC (mL) will be included as a covariate in the analysis model. Other covariates such as age, and gender will be included as covariates unless their inclusion violates model assumptions or impacts stability. Baseline FVC is defined as the FVC result recorded at Visit w0/baseline, unless missing in which case the latest FVC before randomization in the subject's chart result will be used.

The decrease in FVC is assumed to be linear within each subject over 52 weeks. The intercepts and slopes will be assumed to be normally distributed with arbitrary covariance matrix. The within-subject error will be assumed to be independent and normally distributed with mean zero and a common variance. The Kenward-Roger approximation will be used to estimate denominators degrees of freedom.

Section 14.8 details of the approaches to handling of missing data are given.

Significance tests will be based on least-squares means; p-values and two-sided 90% confidence intervals for the difference between the treatment groups will be presented. An intent-to-treat principle will be used. Analyses will be implemented using SAS® Version 9.4 or higher. The assumptions for the primary analysis of decline in FVC will be tested; details will be provided in the SAP. The primary analysis will be based on observed data (but including retrieved drop out

measurements) and will assume remaining missing data are missing at random. The effect of missing data will be investigated using multiple imputation methods which assume that subjects who discontinue treatment will no longer benefit from it in the future. See Section 14.8 for further details of these sensitivity analyses.

Subgroup analyses will be fully specified in the SAP and will include:

- Age
- Gender
- Race
- Ethnicity
- Previous treatment with pirfenidone and/or nintedanib
- Recruitment cohort (e.g., pre- or post- DSMB cutoff, and pre- or post-Protocol version 6.1_UK)

A cumulative distribution plot will be provided, showing the percentage of subjects by change from baseline in FVC in mL at week 52.

Data will be summarized graphically and using summary statistics.

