## 1. INTRODUCTION

This Statistical Analysis Plan (SAP) describes the statistical methods to be used during the reporting and analyses of data collected under protocol GALACTIC-1 (EudraCT Number 2018-002664-73 / IND 124075).

This SAP should be read in conjunction with the Clinical Study Protocol (CSP). This version of the plan has been developed using CSP version 7.0 dated 28 January 2022 [1] and Case Report Form (CRF) version 156 dated Nov 2021 [2]. Any further changes to these documents may necessitate updates to the SAP.

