### 7.2.2 Main Estimand and Analysis

The primary analysis will test for superiority of GB0139 3mg compared to Placebo (Plc) for the annual rate of decline in FVC in mL over 52 weeks in subjects not receiving pirfenidone or nintedanib at baseline in the mITT Set. The main estimand for the primary efficacy endpoint is as follows:

- Population: Primary Population, mITT set.
- Variable of interest: Change from baseline in FVC in mL over 52 weeks
- Intercurrent events:
  - Death: FVC attributed the lowest value recorded in the trial when a patient dies

	Plus-Project Statistical Analysis Plan	
	Protocol Number: GALACTIC-1	Version: 1

- Treatment Discontinuation: Analysis will include any FVC measurements after randomised treatment discontinuation
- Initiation of additional IPF therapy (nintedanib or pirfenidone): Analysis will include any FVC measurements after initiation of additional IPF therapy
- Summary measure: Comparison of slopes assessed through the treatment by time interaction.

The null hypothesis is:

$H_0$ : There is no difference in the annual rate of decline in FVC in mL between GB0139 3mg and Plc

The alternative hypothesis is:

$H_a$  : There is a difference in the annual rate of decline in FVC in mL between GB0139 3mg and Plc

A restricted maximum likelihood (REML) approach will be used, with a random coefficient regression (random slopes and intercepts) model fitted to test the hypotheses. The decrease in FVC is assumed to be linear within each subject over 52 weeks [5].

Baseline FVC and time will be fitted as continuous covariates. The treatment group and the interaction term for time by treatment group will be added as fixed effects. Random subject intercept and time effects will be fitted and will be assumed to be normally distributed with arbitrary covariance matrix. The within-subject errors will be assumed to be independent and normally distributed with mean zero and a common variance. The Kenward-Roger approximation will be used to estimate denominators degrees of freedom.

The statistical model will be as follows:

$$Y_{itk} = (\alpha + a_i + \tau_k) + \beta_f FVCb_i + (\gamma + \beta_3 T_3 + g_i) t + \varepsilon_{it}$$

where:

$Y_{itk}$  is the change from baseline measured for ith patient at time t (actual time) in treatment group k

$t$  is the time since randomization in years

$T_3 = 1$  if the subject is in the GB0139 3mg group, otherwise  $T_3 = 0$

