$\beta_3$  is the effect of treatment on the slope compared to Placebo

$\alpha$  and  $\gamma$  are elements of the intercept and slope respectively

$a_i$  and  $g_i$  are random specific components of the intercept and slope respectively for the ith patient, assumed to be normally distributed with mean 0 and arbitrary covariance matrix

	Plus-Project Statistical Analysis Plan	
	Protocol Number: GALACTIC-1	Version: 1

$FVCb_i$  is the baseline FVC (mL) for the  $i$ th patient

$\tau_k$  is the intercept coefficient of the effect of treatment  $k$  ( $k=1, 2$ )

$\beta_f$  is the effect of 1ml increase in the baseline FVC

$\varepsilon_{it}$  is the random error for  $i$ th patient at time  $t$  assumed to be independent and normally distributed with mean 0 and variance  $\sigma^2$

This approach adopts a missing at random (MAR) assumption (i.e., the probability of an observation being missing depends only on observed measurements). Subjects with missing data at a particular time point still contribute to the analysis at that time point based on their other observed data used in the model (i.e., treatment, baseline FVC, and the FVC at baseline). Data that remain unobserved due to ICEs will be handled as described above. Other missing data will be imputed within the regression model under the MAR assumption.

The linearity assumption for the rate of change in FVC from baseline to week 52 will be explored graphically. Graphical displays will be provided of the mean ( $\pm$  SEM) observed FVC and mean change from baseline for each treatment group by visit.

The assumptions of the analysis will be checked by inspection of graphical displays of the residuals.

A cumulative distribution plot of the percentage of subjects by change from baseline in FVC in mL at week 52 will be presented.

The primary analysis detailed above will be repeated for the Primary Population, PP Analysis Set and for SoC1 / Combination and SoC2 / Monotherapy Populations (only for the mITT Analysis Set).

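### The SAP's SAS row for the primary slope difference returns placebo minus 3 mg, opposite to its label, and prints 95% limits where the protocol requires 90%

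*SAP*

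**What the plan says.** SAP 11.5.1 gives the coding as "trt01pn = Randomized treatment group (1=Placebo, 2= GB0139 3mg". The code then has three ESTIMATE rows. The placebo slope row puts coefficients 1 and 0 on the treatment-by-time interaction. The active row is "estimate '3mg Slope' areltn 1 trt01pn*areltn 0 1/cl". The row for the difference is "estimate 'Slope 3mg v Plc' trt01pn*areltn 1 -1/cl".

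SAP 7.2.2 describes the target as "Summary measure: Comparison of slopes assessed through the treatment by time interaction". Its model sets an indicator to 1 for the 3 mg group and 0 otherwise, and says that the coefficient of that indicator on time (beta_3) "is the effect of treatment on the slope compared to Placebo". The response is change from baseline, which SAP 5.3 defines as the later value minus the baseline value.

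On the interval, Protocol 14.1 sets a two-sided study-wise type I error of 10% and says that "90% confidence intervals are to be calculated, if feasible". Protocol 14.4.1 is specific to the primary endpoint: "p-values and two-sided 90% confidence intervals for the difference between the treatment groups will be presented". SAP 7.2.2 names no confidence level for the primary difference. SAP 7.2.3.1, 7.2.3.3 and 7.2.4.2 name both 90% and 95% for other endpoints. SAP 1 states: "This SAP should be read in conjunction with the Clinical Study Protocol (CSP"). SAP 9, which lists changes from the protocol, records no change of confidence level.

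**The concern.** The row's label and its coefficients point in opposite directions, and its interval is not at the protocol's level.

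**Sign.** A true benefit of 3 mg would appear as a negative number under a label that puts 3 mg first. In the same output the two slope rows would show 3 mg losing less FVC than placebo. The wording makes misreading easier: the endpoint is a rate of decline, where smaller is better, but the model is fitted to change from baseline, where a less negative slope is better. The SAP text does not say which sign favours 3 mg.

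**Interval.** If the row is run as printed, the 90% interval is not produced. A result significant at the planned 10% level could then stand beside an interval that includes zero.

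The same model is to be repeated for the per-protocol set and the SoC1 and SoC2 populations (SAP 7.2.2), the 26-week analyses (7.2.2.1), the subgroups (7.2.2.2), the supplementary analyses (7.2.2.3) and never-treated subjects (7.2.4.10). A copied row would carry both faults into those tables. In the subgroup tables, for which SAP 5 plans no p-values, the estimate and its interval carry the whole comparison.

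**Working it through.** **Inputs.**
- Difference 100 mL, SD 240 mL, two-sided 10% level, N = 141, 2:1 allocation, 75% power (SAP 3.1, Protocol 14.6).
- Placebo decline 200 mL per year (Protocol synopsis).
- Split of 94 on 3 mg and 47 on placebo: an assumption that applies 2:1 to all 141.
- Limits of 95% when `cl` is used without an ALPHA= option: standard SAS behaviour, not stated in the documents.

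**1. The plan's own figure.**
SE = 240 × √(1/94 + 1/47) = 42.88 mL.
Power = Φ(100/42.88 − 1.645) = Φ(0.687) = 0.754. This reproduces the stated 75%, so these inputs are the ones the plan used.

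**2. Direction of the contrast.** Write each row as coefficients on (time, placebo × time, 3 mg × time):

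| Row | Coefficients |
|---|---|
| Placebo slope | (1, 1, 0) |
| 3 mg slope | (1, 0, 1) |
| Difference, as printed | (0, 1, −1) |

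(1, 1, 0) − (1, 0, 1) = (0, 1, −1). The printed difference is exactly the placebo row minus the 3 mg row, which is −beta_3.

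With planning slopes of −200 and −100, and the last level set to zero, the solutions are time = −100 and interaction = (−100, 0).
- Placebo slope: −100 + (−100) = −200.
- 3 mg slope: −100 + 0 = −100.
- Printed difference: 1 × (−100) − 1 × 0 = −100.
- beta_3: −100 − (−200) = +100.

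A random-slope model fitted to one simulated data set of 141 subjects behaved the same way. With fitted slopes of −238.47 (placebo) and −99.94 (3 mg), coefficients (1, −1) gave −138.53 and (−1, 1) gave +138.53. The SE (38.6) and two-sided p-value (0.0003) were the same for both.

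**3. Interval at the planning values.**
- 90% half-width: 1.645 × 42.88 = 70.5 mL.
- 95% half-width: 1.960 × 42.88 = 84.0 mL, a ratio of 1.960/1.645 = 1.19.

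| | Estimate | Limits |
|---|---|---|
| As printed (95%) | −100 | −184.0 to −16.0 |
| Label's direction, protocol's level (90%) | +100 | 29.5 to 170.5 |

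**4. How often the test and the printed interval would seem to disagree.** An estimate favouring 3 mg by between 70.5 and 84.0 mL is significant at 10% but has a 95% interval that includes zero. If the true effect is 100 mL:

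P = Φ((84.0 − 100)/42.88) − Φ((70.5 − 100)/42.88) = 0.109.

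This is the gap between power at the 10% level (0.754) and at the 5% level (0.645).

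**5. Sensitivity to the split.** The Primary Population also contains SoC2 subjects randomized 1:1:1 under the earlier design, so the arms may be closer to equal. At an assumed 71:70:

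SE = 240 × √(1/71 + 1/70) = 40.42 mL, the range becomes 66.5 to 79.2 mL, and P = 0.100.

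**The case against.** The strongest reply is that this is presentational. The p-value, standard error, degrees of freedom and both arm slopes are right, and the slope rows directly above would expose the reversed sign. That is correct, and it limits the weight of the point.

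A second reply is that the label says versus, not minus. If decline is taken as a positive quantity, 3 mg minus placebo is 100 − 200 = −100, which is what the row prints. This does not rescue the row: its label refers to slope, beta_3 is on the slope scale, and the neighbouring rows print slopes without changing their sign. It is fair to add that a careful reader can infer the sign of beta_3 from SAP 5.3 and 7.2.2, so a sentence on direction would be a clarification.

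Third, the 90% interval is already required by the protocol, and the SAP shows 90% and 95% together for other endpoints. This stands in part: a 95% interval is harmless, and the fault is that the 90% interval is missing from the code. Silence in SAP 9 is only modest evidence, because the SAP added 95% intervals for key secondary endpoints without listing that change either. SAP 9 also compares against protocol version 7.0, while the protocol text available for this review refers to version 6.1_UK. The SAP itself keeps the 10% level (3.1), with which a 90% interval agrees.

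Fourth, the code is a fragment: it defines a mean-baseline placeholder that no line uses, and it shows no Day 453 cut-off or death imputation. It is unlikely to be the production program. It is nevertheless the only code the SAP gives for the primary analysis, and the natural template for that program.

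Finally, the 0.109 measures how often an awkward display would arise. It is not the probability of a wrong decision.

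**Conclusion.** The concern holds on both counts. The printed contrast is the negative of the effect the SAP defines and the label implies; this follows from the coding alone and needs no numerical assumption. The code also omits the two-sided 90% interval that Protocol 14.4.1 requires; this rests on the SAS default for `cl` and on the protocol text available.

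At the planning values the estimate would print as −100 instead of +100 mL/year, with an interval 19% wider than the required one. The chance of a 10%-significant result beside a printed interval that includes zero is about 0.10 to 0.11 if the true effect is 100 mL. Those figures assume a normal approximation, the planning SD of 240 mL, and splits between 94:47 and 71:70.

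Type I error, power, sample size and the 10% decision are unaffected. This is a reporting error that should be corrected before database lock; it does not invalidate the primary test.

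**What to change.** In SAP 11.5.1, give the difference row the interaction coefficients `-1 1` with options `/ cl alpha=0.1`. Add a second row at the default level if a 95% interval is also wanted, as for the other endpoints. Put `alpha=0.1` on the two slope rows as well, since Protocol 14.1 asks for 90% intervals generally.

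In SAP 7.2.2, add a sentence stating that the effect is the 3 mg slope minus the placebo slope in mL per year, that a positive value favours 3 mg, and that it is reported with a two-sided 90% interval. Use the same direction and level wherever the primary model is repeated. The SoC1 and SoC2 populations have three arms, so their contrasts should be written out separately.

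The cost is a few characters of code and one sentence, with no effect on data collection, sample size or the test.

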## 11.6 SGRQ Scoring

### 11.6.1 Item Weights

The following weights are applied if the subject gives a positive response as follows:

#### **PART 1 (one response per question)**

##### **1) Over the last year, I have coughed:**

Most 80.6

Several 63.2

A few 29.3

Only 28.1

Not 0.0

##### **2) Over the last year, I have brought up phlegm (sputum):**

Most 76.8

Several 60.0

A few 34.0

Only 30.2

Not 0.0

##### **3) Over the last year, I have had shortness of breath:**

Most 87.2

Several 71.4

A few 43.7

Only 35.7

Not 0.0

##### **4) Over the last year, I have had attacks of wheezing:**

Most 86.2

Several 71.0

A few 45.6

Only 36.4

Not 0.0

##### **5) During the last year, how many severe or very bad unpleasant attacks of chest trouble have you had?**

More than three 86.7

3 attacks 73.5

2 attacks 60.3

1 attack 44.2

None 0.0

##### **6) How long did the worst attack of chest trouble last?**

a week or more 89.7

3 or more days 73.5

	Plus-Project Statistical Analysis Plan	
	Protocol Number: GALACTIC-1	Version: 1

1 or 2 days 58.8  
less than a day 41.9

**7) Over the last year, in an average week, how many good days (with little chest trouble) have you had?**

None 93.3  
1 or 2 76.6  
3 or 4 61.5  
nearly every day 15.4  
every day 0.0

**8) If you have a wheeze, is it worse in the morning?**

No 0.0  
Yes 62.0

**PART 2**

**9) How would you describe your chest condition? (one response)**

The most important problem I have 83 .2  
Causes me quite a lot of problems 82.5  
Causes me a few problems 34.6  
Causes no problem 0.0

**10) If you have ever had paid employment? (one response)**

My chest trouble made me stop work 88.9  
My chest trouble interferes with my work or made me change my work 77.6  
My chest trouble does not affect my work 0.0

**11) Questions about what activities usually make you feel breathless (all that apply).**

Sitting or lying still 90.6  
Getting washed or dressed 82.8  
Walking around the home 80.2  
Walking outside on the level 81.4  
Walking up a flight of stairs 76.1  
Walking up hills 75.1  
Playing sports or games 72.1

**12) More questions about your cough and breathlessness (all that apply).**

My cough hurts 81.1  
My cough makes me tired 79.1  
I get breathless when I talk 84.5  
I get breathless when I bend over 76.8  
My cough or breathing disturbs my sleep 87.9  
I get exhausted easily 84.0

	Plus-Project Statistical Analysis Plan	
	Protocol Number: GALACTIC-1	Version: 1

**13) Questions about other effects your chest trouble may have on you (all that apply).**

- My cough or breathing is embarrassing in public 74.1
- My chest trouble is a nuisance to my family, friends or neighbours 79.1
- I get afraid or panic when I cannot get my breath 87.7
- I feel that I am not in control of my chest problem 90.1
- I do not expect my chest to get any better 82.3
- I have become frail or an invalid because of my chest 89.9
- Exercise is not safe for me 75.7
- Everything seems too much of an effort 84.5

**14) Questions about your medication (all that apply).**

- My medication does not help me very much 88.2
- I get embarrassed using my medication in public 53.9
- I have unpleasant side effects from my medication 81.1
- My medication interferes with my life a lot 70.3

**15) Questions about how activities may be affected by your breathing (all that apply).**

- I take a long time to get washed or dressed 74.2
- I cannot take a bath or shower, or I take a long time 81.0
- I walk more slowly than other people, or I stop for rests 71.7
- Jobs such as housework take a long time, or I have to stop for rests 70.6
- If I walk up one flight of stairs, I have to go slowly or stop 71.6
- If I hurry or walk fast, I have to stop or slow down 72.3
- My breathing makes it difficult to do things such as walk up hills, carry things up stairs, light gardening such as weeding, dance, play bowls or play golf 74.5
- My breathing makes it difficult to do things such as carry heavy loads, dig the garden or shovel snow, jog or walk at 5 miles per hour, play tennis or swim 71.4
- My breathing makes it difficult to do things such as very heavy manual work, run, cycle, swim fast or play competitive sports 63.5

**16) We would like to know how your chest trouble usually affects your daily life (all that apply).**

- I cannot play sports or games 64.8
- I cannot go out for entertainment or recreation 79.8
- I cannot go out of the house to do the shopping 81.0
- I cannot do housework 79.1
- I cannot move far from my bed or chair 94.0

**17) Tick the statement which you think best describes how your chest affects you (tick one).**

- It does not stop me doing anything I would like to do 0.0
- It stops me doing one or two things I would like to do 42.0
- It stops me doing most of the things I would like to do 84.2
- It stops me doing everything I would like to do 96.7

	Plus-Project Statistical Analysis Plan	
	Protocol Number: GALACTIC-1	Version: 1

### 11.6.2 Scoring

The weights from each question included in each component will be summed as follows:

Symptoms Component: questions 1-8 (max score 662.5).

Activity Component: questions 11 and 15 (max score 1209.1).

Impacts Component: questions 9-10, 12-14 and 16-17 (max score 2117.8).

Total Score: questions 1-17 (max score 3989.4).

Each component score will be calculated as:  $100 \times \text{Summed weights for each question in that component} / \text{max score}$

If multiple responses are given in error then the average weight will be used for the question.

If there are missing items (depending on expected response), the maximum weight for the missing item will be subtracted from the max score in the denominator. The maximum number allowable missing items in each component are as follows: Symptoms Component – 2 items, Activity Component – 4 items, Impacts Component – 6 items.

	Plus-Project Statistical Analysis Plan	
	Protocol Number: GALACTIC-1	Version: 1

